7.2.2 Safety Secondary Endpoints

Because the infusion of hMSCs could theoretically, as described above, cause transient occlusion of the pulmonary microcirculation which could be associated with a fall in systemic blood pressure, rising vasopressor dose, a rise in heart rate, an increase in arterial carbon dioxide concentration, or a fall in oxygenation, patients will be monitored closely during the study infusion for changes in these parameters. These events will be considered pre-specified infusion associated events if they occur within 6 hours of the study product infusion.

Pre-specified infusion associated events will be defined as:

1. Within 6 hours of the initiation of study product infusion:

- An increase in vasopressor dose greater than or equal to the following:
 - Norepinephrine: 10 mcg/min
 - Phenylephrine: 100 mcg/min
 - Dopamine: 10 mcg/kg/min
 - Epinephrine: 0.1 mcg/kg/min
 - Addition of a third vasopressor
- New ventricular tachycardia, ventricular fibrillation or asystole
- New cardiac arrhythmia requiring cardioversion
- Hypoxemia requiring an increase in FiO₂ of 0.2 or more and an increase in PEEP of 5 cmH₂O or more to maintain SpO₂ in the target range of 88-95% that is not related to respiratory care/suctioning or ventilator dyssynchrony and persists for more than 30 minutes
- Clinical scenario consistent with transfusion incompatibility or transfusion-related infection (e.g. urticaria, rash, new bronchospasm)

2. Within 24 hours of the study product infusion:

- Any cardiac arrest or death

We will also systemically collect and review the incidence and nature of serious adverse events that are different from what is expected in the clinical course of a critically ill patient with ARDS for the duration of the clinical trial (through day 28 from study product infusion).

Expected events for ARDS are untoward clinical occurrences that are perceived by the investigator to occur with reasonable frequency in the day to day care of patients with ARDS treated in an intensive care unit with mechanical ventilation. Examples of adverse events that are expected in the course of ARDS include transient hypoxemia, agitation, delirium, nosocomial infections, skin breakdown, and gastrointestinal bleeding. Such events, which are often the focus of prevention efforts as part of usual ICU care, will not be considered reportable adverse events unless the event is considered by the investigator to be associated with the study drug or procedures, or unexpectedly severe or frequent for an individual patient with ARDS. Examples of unexpectedly frequent adverse events would be repeated episodes of unexplained hypoxemia. This would be in contrast to an isolated episode of transient hypoxemia (e.g. SpO₂ ~85%), related to positioning or suctioning. This latter event would not be considered unexpected by nature, severity or frequency.

For this Phase 2b study, the secondary safety endpoint will be the incidence of pre-specified infusion associated events occurring within 6 hours of study product administration and any cardiac arrest or death occurring within 24 hours of study product administration, as well as any unexpected severe adverse events in ARDS patients (not including death because it is expected in ARDS) treated with hMSCs compared to patients treated with placebo through day 28 after study product administration.

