Thus, for the last four sheep, we continued to use this more moderate dose of bacteria, but returned to the original approach of administration of the hMSCs after washing them to remove all the DMSO and without any pre-treatment with Benadryl or hydrocortisone. In the final four sheep (MSC-treated and control-treated pairs), there was evidence of efficacy of improved oxygenation ($\text{PaO}_2/\text{FiO}_2$ ratio) as in the prior group 1 experiments from 2011. However, there was still evidence that the second dose of hMSCs given at eighteen hours was not tolerated, because one of the hMSC-treated sheep died prior to 24 hours.

We previously concluded from these studies that (1) DMSO should not be used in our clinical trial and (2) that we could not demonstrate preclinical safety for a second dose of hMSCs in this severe model of ALI when the hMSCs were given only 18 hours after the lung injury following an initial dose of hMSCs at 1 hour following the injury.

As discussed further in this clinical protocol, based on the results of the phase 2a clinical trial in 60 patients (START trial), the process of removing DMSO with an extra wash step did reduce hMSC viability. Therefore, in this phase 2b trial, we will simplify the bone marrow transplant procedures and not remove the DMSO after thawing the hMSCs product for clinical administration. The product will be thawed and diluted with 1:1 mix of 5% human serum albumin and 10% Dextran 40 (see Study Product Preparation Protocol in Appendix E).

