12.1 Definitions

Investigators will determine daily if any clinical adverse experiences occur during the period from enrollment through study day 28 after investigational product administration. The investigator will evaluate any changes in laboratory values or physical signs, and will determine if the change is clinically important and different from what is expected in the course of treatment of patients with ARDS.

For this trial, a reportable adverse event is defined as:

Any clinically important untoward medical occurrence in a patient receiving study product which is different from what is expected in the clinical course of a patient with ARDS, or:

1. Any clinically important, untoward medical occurrence that is thought to be associated with the study product, regardless of the “expectedness” of the event for a patient with ALI, or
2. The following pre-specified infusion associated events occurring within 6 hours from the start of study product will always be reported as adverse events:

- If on a vasopressor, an increase in vasopressor dose greater than or equal to the following:
 - Norepinephrine: 10 mcg/min
 - Phenylephrine: 100 mcg/min
 - Dopamine: 10 mcg/kg/min
 - Epinephrine: 0.1 mcg/kg/min
 - Addition of a third vasopressor
- New cardiac arrhythmia requiring cardioversion OR ventricular tachycardia, ventricular fibrillation or asystole
- Hypoxemia requiring an increase in FiO₂ of 0.2 or more and an increase in PEEP of 5 cmH₂O or more to maintain SpO₂ in the target range of 88-95% that is not related to respiratory care/suctioning or ventilator dyssynchrony and persists for more than 30 minutes
- Clinical scenario consistent with transfusion incompatibility or transfusion-related infection (e.g. urticaria, new bronchospasm)

3. Any cardiac arrest or death that occurs within 24 hours from the start of study product will be reported as a pre-specified, infusion-associated significant event. Any cardiac arrest or death that occurs during the study period will be a reportable event that will be reviewed in detail.

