12.5 Stopping Rules

The DSMB will review post-infusion safety data after 60 subjects have been enrolled and received study product; however, enrollment will not be suspended pending DSMB review. The study will be stopped for a safety evaluation by the DSMB if they have any concerns or if three subjects have

pre-specified clinically important events or unexpected serious adverse events EXCEPT death since death will be common in this critically ill population due the nature of the underlying illness (e.g., ARDS).

The study will end when 120 patients have been recruited and received the study product and have all completed 60-day follow-up, after which data analysis will commence. This Phase 2b study will stop prior to completion if mandated by the Department of Defense-appointed DSMB or the FDA due to safety concerns.

12.6 *Medical Monitoring*

It is the responsibility of the Principal Site Investigator at each of the 7 hospital sites to oversee the safety of the study at his/her site. This safety monitoring will include careful assessment and appropriate reporting of adverse events as noted above, as well as the construction and implementation of a site data and safety-monitoring plan. Medical monitoring will include a regular assessment of the number and type of serious adverse events. The study will have an independent DSMB to oversee serious adverse events.

12.6.1 *Independent Data and Safety Monitoring Board*

This Phase 2b study will be monitored by an independent DSMB. The DSMB will contain 3 members. There will be 2 intensivists familiar with the care of critically ill patients and ARDS, at least one of whom will be familiar with the care of critically ill patients who have suffered trauma. There will also be a biostatistician. A DSMB Charter will define the DSMB's responsibilities as described below.

The DSMB will meet by teleconference at the planned interim safety analysis (60 patients) for this Phase 2b trial. At this meeting, the DSMB will review all safety data in aggregate; individual adverse event narratives will also be available to the DSMB for review. During the trial, the DSMB will review the safety data in an unblinded fashion. The DSMB will also receive reports of serious, unexpected, and study-related adverse events and unanticipated problems on an ongoing basis.

The actual analyses will be conducted by the Clinical Coordinating Center Biostatistician who will be blinded to the randomization scheme.

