Appendix F: Symptom Management During Infusion Guidelines

Adverse Reactions	Signs and Symptoms	Management
reactions are usually symptomatic and occasionally life-threatening.	
 • Disseminated-intravascular coagulation 	
 • Send recipient blood for a “transfusion reaction analysis” to the blood bank. • Consider mannitol 25 gm IV if suspicion of a transfusion ABO incompatibility reaction is high. • Consider blood cultures (and culture of the MSC product) followed by broad spectrum anti-bacterial antibiotics. • The attending BMT physician will be informed of the episode and will decide whether to restart the MSC infusion or abort the MSC infusion. • If the MSC infusion is aborted, the balance of the MSC product will be quarantined in the BMT laboratory refrigerator for possible additional analysis.
Reactions to Cryopreservatives (e.g. DMSO) DMSO is added to all MSC products being cryopreserved to protect the MSC from hypothermal damage.	
 • Metallic/garlic taste • Nausea/emesis • Flushing of face • Intestinal cramps • Acute hypertension • Bradycardia (first, second, or third degree atrioventricular block on electrocardiogram) 	
 • Pause MSC infusion. • Check vital signs and O2 saturation. • Administer additional anti-emetics if appropriate. • If bradycardia, perform an electrocardiogram. If patient is asymptomatic with first or second degree atrio-ventricular block on EKG, resume MSC infusion. If symptomatic, stop infusion and administer atropine 0.5 -1mg. • If bradycardia is present and electrocardiogram shows third degree atrio-ventricular block, consider placement of a temporary pacemaker. Consult Cardiology. • Infuse remainder of previously non-thawed MSC after reasonable resolution of the signs and symptoms of an acute DMSO reaction and acquisition of hemodynamic stability.
Infection/Endotoxemia	
 • Hypotension 	
 • Stop the MSC infusion

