- B. The initial dose was 1×10^6 cells/kg given intravenously to 3 patients. After approval from the DSMB, we progressed to the next dose. The second dose delivered was 5×10^6 cells/kg given intravenously to 3 patients. The third dose level was 10×10^6 cells/kg given intravenously to 3 patients.

In the **Phase 2a trial**, we enrolled 60 patients in a 2:1 blinded randomized placebo-controlled design with the dose of 10×10^6 cells/kg (40 patients treated with hMSCs and 20 controls). Safety analyses was conducted by the independent DSMB, and the sponsor and investigators were blinded.

The initial phase 1 and 2a trials were designed to test hMSCs for medical causes of ARDS, with a plan to exclude trauma-related ARDS. [name] and his co-investigators reasoned that the trauma population should be included in a subsequent trial because the mechanisms of lung injury in trauma-related ARDS have several common pathways to medical causes of lung injury, although some trauma patient have hypovolemic shock from penetrating or blunt trauma, ischemia-reperfusion following fluid resuscitation, multiple blood product transfusions, pulmonary contusion and long bone fractures. This is the rationale of testing hMSCs for both trauma and medical causes of ARDS.

In this context, we will test allogeneic hMSCs in the moderate to severe ARDS populations from both medical and trauma reasons in a randomized, double-blinded, placebo-controlled Phase 2b clinical trial, using a 10×10^6 cell/kg predicated body weight (PBW) dose of hMSCs product derived from bone marrow by conventional methods.

The allogeneic bone marrow-derived human mesenchymal stromal cells (hMSCs) for this trial are manufactured at University of Minnesota's Molecular & Cellular Therapeutics (MCT) Facility. The hMSCs are formulated in CryoStor (90%) and DMSO (10%), and cryopreserved and stored in

bags suspended in liquid nitrogen. Immediately prior to administration, the hMSCs will be thawed and diluted in 1:1 reconstitution media (1:1 mix of 5% human serum albumin and 10% Dextran 40). Additional reconstitution media will be added to a final product volume of 300 mL. The placebo group will be treated with 300 mL of reconstitution media (1:1 mix of 5% human serum albumin and 10% Dextran 40).

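### The infusion-event list has no bradycardia or AV-block item, although Appendix F names this as a sign of a cryopreservative reaction and only the hMSC arm receives DMSO

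*SAP*

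**What the plan says.** **The list.** SAP 7.2.2 and Protocol 6.2.2 define the pre-specified events within 6 hours of starting the infusion. The rhythm items are "New ventricular tachycardia, ventricular fibrillation or asystole" and "New cardiac arrhythmia requiring cardioversion"; Protocol 12.1 merges them as "New cardiac arrhythmia requiring cardioversion OR ventricular tachycardia, ventricular fibrillation or asystole". The other items are a vasopressor rule ("An increase in vasopressor dose greater than or equal to the following", with thresholds by drug, or a third vasopressor), hypoxemia, and a transfusion-type reaction. Cardiac arrest or death counts within 24 hours.

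**Appendix F.** Under reactions to cryopreservatives such as DMSO it lists six signs. One is "Bradycardia (first, second, or third degree atrioventricular block on electrocardiogram". The management column covers an electrocardiogram, atropine and a temporary pacemaker, depending on grade and symptoms.

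**Exposure.** Protocol 3.4 says that this trial will "not remove the DMSO after thawing the hMSCs product for clinical administration", because the wash step used in phase 2a reduced cell viability. On the control side, SAP 3 states: "The placebo group will be treated with 300 mL of reconstitution media". That medium is albumin and Dextran 40, with no DMSO.

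**What the list feeds.** Listed events form the first part of the safety endpoint (Protocol 6.2.2, SAP 7.2.2); unexpected severe adverse events to day 28 form the second. Protocol 12.5 stops the study for a DSMB safety evaluation if three subjects have "pre-specified clinically important events or unexpected serious adverse events EXCEPT death". Under Protocol 12.1 listed events are always reported. Under Protocol 9.4 F, repeated in SAP 5, a listed event also stops the infusion.

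**The concern.** The stated rationale for the list is transient occlusion of the pulmonary microcirculation: falling blood pressure, rising vasopressor dose, rising heart rate, worse gas exchange. The cryopreservative reaction in Appendix F differs, with bradycardia and acute hypertension among its signs. A list built for the first hazard does not automatically cover the second.

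This matters because exposure to DMSO differs completely by arm, and because the absence of pre-specified infusion events in phase 2a (Protocol 3.6) was observed with a washed product. That earlier result says little about retained DMSO. Phase 2b is where such a signal could be seen against a concurrent control, and Appendix F names a sign that a bedside monitor can show in a ventilated patient. If the sign is counted only when a blinded investigator classifies it in a particular way, the two arms may be compared on an incomplete count.

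**Working it through.** No figure in the plan needs reproducing. The check traces cases of new bradycardia or AV block within 6 hours through the rules.

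| Case | Pre-specified list | Second part of safety endpoint | Three-subject count | General AE tables |
|---|---|---|---|---|
| Mild block, infusion paused and resumed | No item | Not if judged not severe | Not if judged not serious | Yes, if reported |
| Block treated with atropine | No item | Only if judged unexpected and severe | Only if judged unexpected and serious | Yes, if reported |
| High-grade block, pacing considered | No item | Plausibly, by judgement | Plausibly, by judgement | Yes, if reported |
| Progression to asystole, arrest or a vasopressor threshold | **Yes** | Not needed | Yes, reading its pre-specified events as this list | Yes |

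1. *Rhythm items.* Atropine and pacing are not cardioversion, and AV block is not ventricular tachycardia, ventricular fibrillation or asystole. The first three rows therefore meet no rhythm item.
2. *Vasopressor item.* An epinephrine or dopamine increase at threshold would bring a case onto the list. This is a weak fallback for a reaction described with acute hypertension. Protocol 12.1 also limits the item to patients already on a vasopressor, a condition absent from Protocol 6.2.2 and SAP 7.2.2.
3. *Transfusion item.* It names incompatibility and infection, not a cryopreservative reaction.
4. *Expectedness.* Protocol 6.2.2 and 12.1 and SAP 7.2.2 judge adverse events against the usual course of ARDS. The unanticipated-problem definition, also in Protocol 12.1, judges against the protocol documents. Nothing says expressly which standard applies to an Appendix F reaction in the safety endpoint or the three-subject count.
5. *General tables.* SAP 12.7.11 collects all adverse events, lists them individually, and compares serious and non-serious events between arms by organ system over 28 days. A cardiac total over 28 days does not isolate a 6-hour rhythm event.

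*Exposure, for scale.* Assume 70 kg predicted body weight and bags at 5–10 × 10⁶ cells/mL (Protocol 8.2 gives 1–10). Product volume = 10 × 10⁶ × 70 ÷ (5 to 10 × 10⁶) = 140 to 70 mL. At 10% DMSO this is 14 to 7 mL, or 4.7% to 2.3% of 300 mL before the quality-control draw. Placebo receives 0 mL.

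*Why no magnitude is given.* For an assumed event rate p among 60 hMSC patients,

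P(X ≥ 3) = 1 − Σₖ₌₀² C(60,k) pᵏ(1−p)⁶⁰⁻ᵏ.

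At p = 0.05 this is 1 − (0.046 + 0.145 + 0.226) = 0.58. At 1%, 3% and 10% it is 0.02, 0.27 and 0.95. A range from 0.02 to 0.95 tells the reader nothing without a rate.

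*What a separate line can do.* Fisher's exact test (two-sided) gives p = 0.24 for 3/60 against 0/60, 0.057 for 5 against 0, and 0.027 for 6 against 0. The gain is a complete count for the DSMB and the report, rather than a significance test.

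**The case against.** A reader might infer that AV block cannot register anywhere in the safety data. The documents do not support that. Protocol 12.1 makes reportable any clinically important event that differs from the expected course of ARDS, and any such event thought to be linked to the product whatever its expectedness. SAP 12.7.11 compares adverse events between arms. The worst cases reach the list through asystole, arrest or vasopressor use.

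A reader might also infer that naming the reaction in Appendix F makes it expected and so excludes it from the safety endpoint. The adverse-event rules point the other way: their benchmark is the course of ARDS, and their examples (transient hypoxemia, agitation, delirium, nosocomial infection, skin breakdown, gastrointestinal bleeding) do not include heart block. High-grade block considered for pacing could well qualify as an unexpected serious event. The second standard in Protocol 12.1 leaves an ambiguity, not an exclusion.

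Three further points stand. AV block is one of six Appendix F signs, in a symptom-management guide that gives no incidence. The DSMB may act on any concern, and the Research Monitor may stop the protocol (Protocol 14.1), so the count of three is not the only safeguard. And simply adding the item to the list would activate the infusion stop in Protocol 9.4 F, where Appendix F provides for resuming in some cases.

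The objection does not remove the difference between an event that is always reported and one that depends on a blinded investigator's view of importance, severity and expectedness.

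**Conclusion.** The concern holds as a gap in systematic counting. Bradycardia or AV block short of asystole, arrest or a vasopressor threshold has no place on the pre-specified list. It enters the safety endpoint or the three-subject count only by judgement, and milder cases are seen only within organ-system totals. The sign is one that the protocol itself attributes to cryopreservative, which only one arm receives and which the phase 2a wash step was meant to remove.

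The conclusion rests on the text alone. It does not depend on any assumed event rate, and none is offered. It does not show that the safety comparison misses the reaction altogether, or that the three-subject review would have been reached.

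**What to change.** 1. In Protocol 12.1 and SAP 7.2.2, make new bradycardia or AV block within 6 hours of starting the infusion, when it leads to treatment or to interruption of the infusion, an always-reported event. For now, place it as a separate item beside the pre-specified list, so that it does not activate the stop in Protocol 9.4 F and SAP 5.
2. In SAP 12.7.11, tabulate this event by arm on its own line, with counts, percentages and the between-arm comparison already planned for adverse events.
3. State in Protocol 12.1 and SAP 7.2.2, with a pointer from Protocol 6.2.2 and 12.5, that expectedness for the safety endpoint and the three-subject count is judged against the course of ARDS, so that appearing in Appendix F does not make an event expected.
4. Ask the clinical team to reconcile Protocol 9.4 F (a pre-specified event stops the infusion) with Appendix F (pause, and in some cases resume) before the item is moved onto the list that governs stopping. This point proposes no clinical rule; it concerns counting and reporting only.

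The cost is a few lines of text and one CRF item. Rhythm is already monitored continuously during the infusion (Protocol 9.4 F), and heart rate is recorded every 15 minutes during it and hourly for the next 5 hours (Protocol 10.3). The downside is that a DSMB review might come somewhat earlier.

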7.2.3 Primary and Secondary Endpoints Adjusted for SARS-CoV-2 Infection

In addition, to better understand the hMSC effects in patients with COVID-19 disease, we will conduct the following analyses:

- The primary and secondary endpoints as stratified in separate analyses by the following binary variables of interest prior to randomization: SARS-CoV-2 Infection status, viral antigen level (greater or less than median value), dexamethasone (or equivalent steroid therapy) and other immunomodulatory agents.
- WHO Scale for Clinical Improvement outcome at baseline, day 7, day 14, and day 28 adjusted by COVID-19 status.
- Gene expression profiles compared by treatment arm and adjusted for or stratified by SARS-CoV-2 Infection, dexamethasone (or equivalent steroid therapy) and other immunomodulatory agents.
- Changes in levels of protein biomarker measurements by treatment arm and adjusted for or stratified by SARS-CoV-2 infection, dexamethasone (or equivalent steroid therapy), and other immunomodulatory agents.
- Analysis of primary and secondary endpoints by latent class analysis (LCA) subphenotype and adjusted for or stratified by SARS-CoV-2 Infection.
- Analyses of primary and secondary endpoints adjusted for or stratified by anticoagulation and antiplatelet treatments.
- Analyses to be adjusted for measures of MSC viability.

